#### **2.4.4.3 Multiplicity issues**

In order to handle the key secondary efficacy endpoint, the overall type-I error will be controlled by the use of a sequential inferential approach. Statistical significance of the primary efficacy endpoint at the 0.05 alpha level is required before drawing inferential conclusions about the key secondary efficacy endpoint (defined in [Section 2.1.3.2.1](#)). This fixed hierarchical approach will ensure a strong control of the overall type-I error rate at the 0.05 level.

No further adjustments will be made for other secondary endpoints other than key secondary endpoint for which p-values will be provided for exploratory purpose only (no claim).

#### **2.4.5 Analyses of safety data**

The summary of safety results will be presented by treatment group.

##### ***General common rules***

All safety analyses will be performed on the safety population as defined in [Section 2.3.2](#), unless otherwise specified, using the following common rules:

- Safety data in patients who do not belong to the safety population (eg, exposed but not randomized) will be listed separately;
- The baseline value is defined as the last available value before randomization, unless otherwise specified;
- The potentially clinically significant abnormality (PCSA) values are defined as abnormal values considered medically important by the Sponsor according to predefined criteria/thresholds based on literature review and defined by the Sponsor for clinical laboratory tests, vital signs (PCSA defined in the document “Analysis and reporting safety data from clinical trials through the Clinical Study Report (CSR) (Version Number: 3.0)” [\[Appendix A\]](#))
- PCSA criteria will determine which patients had at least 1 PCSA during the TEAE period, taking into account all evaluations performed during the TEAE period, including nonscheduled or repeated evaluations.
- The treatment-emergent PCSA denominator by group for a given parameter will be based on the number of patients assessed for that given parameter in the TEAE period by treatment group on the safety population.
- All measurements, scheduled or unscheduled, fasting or not fasting, will be assigned to analysis windows defined in [Section 2.5.4.2, Table 4](#).
- For quantitative safety parameters, descriptive statistics will be used to summarize results and change from baseline values by visit and treatment group using analysis windows defined in [Section 2.5.4.2, Table 4](#). Summaries will include the last on-treatment value and the worst on-treatment value. The worst value is defined as the nadir and/or the peak value during the treatment period according to the direction (minimum or maximum) of the abnormality as defined in the PCSA list.

Analyses performed according to diabetic status will be done using the CMQ definition (regardless of the ongoing status) ([Section 2.1.1](#)).

#### **2.4.5.1 Analyses of adverse events**

##### ***Generalities***

The primary focus of AE reporting will be on TEAEs. Pre-treatment and post-treatment AEs will be described separately.

If an AE date/time of onset (occurrence, worsening, or becoming serious) is incomplete, an imputation algorithm will be used to classify the AE as pre-treatment, treatment-emergent, or post-treatment. The algorithm for imputing date/time of onset will be conservative and will classify an AE as treatment-emergent unless there is definitive information to determine it is pre-treatment or post-treatment. Details on classification of AEs with missing or partial onset dates are provided in [Section 2.5.3](#).

AE incidence tables will present, the number (n) and percentage (%) of patients experiencing an AE by SOC, HLTG (when applicable), HLT (when applicable), and PT. Multiple occurrences of the same event in the same patient will be counted only once in the tables within a treatment phase. The denominator for computation of percentages is the safety population within each treatment group.

Sorting within tables ensures the same presentation for the set of all AEs within the observation period (pre-treatment, TEAE, and post-treatment). For that purpose, the table of all TEAEs presented by SOC and PT sorted by the internationally agreed SOC order and decreasing frequency of PTs within SOCs (in the alirocumab group) will define the presentation order for all other tables by SOC and PT, unless otherwise specified. The tables of AEs by SOC, HLTG, HLT and PT will be sorted by the SOC internationally agreed order and the other levels (HLTG, HLT, and PT) will be presented in alphabetical order, unless otherwise specified

##### ***Analysis of all treatment-emergent adverse events***

The following TEAE summaries will be generated for the safety population.

- Overview of TEAEs, summarizing number (%) of patients with any:
  - TEAE;
  - Treatment emergent serious adverse event (SAE);
  - TEAE leading to death;
  - TEAE leading to permanent treatment discontinuation.
- All TEAEs by primary SOC, HLTG, HLT, and PT, sorted by the SOC internationally agreed order. The other levels (HLTG, HLT, and PT) will be presented in alphabetical order;

- All TEAEs regardless of relationship and related to IMP by primary SOC, HLT, and PT, sorted by the internationally agreed SOC order. The other levels (HLGT, HLT, and PT) will be presented in alphabetical order;
- All TEAEs regardless of relationship and related to LMT-NIMP by primary SOC, HLT, and PT, sorted by the internationally agreed SOC order. The other levels (HLGT, HLT, and PT) will be presented in alphabetical order;
  - AE related to LMT-NIMP is defines all AEs checked “Related” in “Atorvastatin/Rosuvastatin?” or “Lipid Modifying Therapy?” on the adverse event case report form page.
- All TEAEs regardless of relationship and related to LMTs by primary SOC, HLT, and PT, sorted by the internationally agreed SOC order. The other levels (HLGT, HLT, PT) will be presented in alphabetical order;
  - AE related to LMTs is defines all AEs checked “Related” in “IMP/Praluent?”, or “Atorvastatin/Rosuvastatin?”, or “Lipid Modifying Therapy?” on the adverse event case report form page.
- All TEAEs by primary SOC and PT, sorted by the internationally agreed SOC order and by decreasing incidence of PTs within each SOC (in the alirocumab group). This sorting order will be applied to all other tables by SOC and PT of TEAEs, unless otherwise specified.
- The frequency of AEs by SOC/PT and selected AEs over time during TEAE period (number of patients experiencing AE and percentage by patient-months) will be provided by time intervals defined as:  $\leq 12$  weeks,  $>12$  to  $\leq 24$  weeks,  $>24$  weeks using the actuarial method. Only the first event will be counted. Those intervals will be calculated from the randomization.
- All TEAEs that occurred with HLT incidence  $\geq 2\%$  in any treatment group, by primary SOC, HLT, and PT, sorted by internationally agreed SOC order and by alphabetic order for the other levels (HLT and PT);
- All TEAEs by maximal intensity (ie, mild, moderate, or severe), presented by primary SOC and PT.

#### ***Analysis of all treatment emergent serious adverse event(s)***

- All treatment-emergent SAEs by primary SOC, HLT, and PT, sorted by the internationally agreed SOC order. The other levels (HLGT, HLT, and PT) will be presented in alphabetical order;
- All treatment-emergent SAEs regardless of relationship and related to IMP, by primary SOC, HLT, and PT, sorted by the internationally agreed SOC order. The other levels (HLGT, HLT, and PT) will be presented in alphabetical order.
- All treatment-emergent SAEs regardless of relationship and related to LMT-NIMP, by primary SOC, HLT, and PT, sorted by the internationally agreed SOC order. The other levels (HLGT, HLT, and PT) will be presented in alphabetical order.

- All treatment-emergent SAEs regardless of relationship and related to LMTs, by primary SOC, HLGT, HLT, and PT, sorted by the internationally agreed SOC order. The other levels (HLGT, HLT, and PT) will be presented in alphabetical order.
- All treatment-emergent SAEs by primary SOC and PT.

#### ***Analysis of all treatment-emergent adverse event(s) leading to treatment discontinuation***

- All TEAEs leading to treatment discontinuation, by primary SOC, HLGT, HLT, and PT, sorted by the internationally agreed SOC order. The other levels (HLGT, HLT, and PT) will be presented in alphabetical order.
- All TEAEs leading to treatment discontinuation by primary SOC and PT;

#### ***Analysis of groupings of adverse events including selected adverse events of special interest***

All grouping of TEAEs including adverse events of special interest as listed in [Section 2.1.4.1](#) will be analyzed using selections defined in [Section 2.1.4.1](#) and will be presented by SMQ and PT (when selection is based on SMQs) and by SOC and PT (when selection is based on the e-CRF tick box or HLGT/HLT). The summaries will be sorted by decreasing incidence of PT within each SOC/SMQ (in the alirocumab group).

Analyses of grouping of AEs for diabetes ([Section 2.1.4.1](#)) will be performed overall and according to the diabetic status at baseline ([Section 2.1.1](#)).

In addition, the following variables will be tabulated for the local injection site reactions TEAEs:

- Intensity of the event (mild, moderate, severe);
- Number of events divided by the number of IMP injections received;
- Time from randomization to first injection site reaction;
- Description of the highest intensity of each symptom recorded in the specific e-CRF page with table and bar chart.

Besides, description of symptoms and possible etiologies for General Allergic Reaction TEAE reported by investigator (using the tick box), will be presented.

#### ***Analysis of cardiovascular events***

Adjudication results of treatment-emergent CV events will be summarized.

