	Dose regimen approved in Japan: 75 mg Q2W with up-titration to 150 mg Q2W if LDL-C <100 mg/dL is not achieved.

[figure not shown]
Noninvestigational medicinal product(s)	
• Atorvastatin• Rosuvastatin• Cholesterol absorption inhibitor (ezetimibe)• Fibrates (fenofibrate, bezafibrate)• Anti-platelets (aspirin, clopidogrel, etc.)• Warfarin, and other oral anticoagulants approved in Japan
Route(s) of administration:	Oral
Dose regimen:	Dose regimen approved in Japan
ENDPOINT(S)	
Primary efficacy endpoint:
 
• Percent change in normalized TAV from baseline to Week 36 
Key secondary efficacy endpoint:
 
• Absolute change in PAV from baseline to Week 36 
Other secondary efficacy endpoint(s):
 
• Absolute change in normalized TAV from baseline to Week 36• Absolute and percent change in external elastic membrane (EEM) volume from baseline to Week 36• Absolute and percent change in lumen volume from baseline to Week 36• Absolute and percent change in calculated LDL-C from baseline to Week 12, and Week 36• Absolute and percent change in Apo B from baseline to Week 36• Absolute and percent change in non-HDL-C from baseline to Week 36• Absolute and percent change in total cholesterol (TC) from baseline to Week 36• Absolute and percent change in Lp(a) from baseline to Week 36• Absolute and percent change in HDL-C from baseline to Week 36• Absolute and percent change in fasting triglycerides (TGs) from baseline to Week 36• Absolute and percent change in apolipoprotein A-1 (Apo A-1) from baseline to Week 36 
Safety endpoints:
 
• Safety parameters (adverse events including CV events*, laboratory data and vital signs) assessed throughout the study

	
*CV events: CHD death, non-fatal MI, fatal and non-fatal ischemic and/or haemorrhagic stroke, unstable angina requiring hospitalization, congestive heart failure requiring hospitalization, ischemia-driven coronary revascularization.

ASSESSMENT SCHEDULE	
Patient's assessments in the treatment period: On-site visits: Week 0 (randomization visit), Week 4, Week 12, Week 24, Week 36

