	
efficacy endpoint will be tested at the two-sided 5% level. The other secondary efficacy endpoints not included in key secondary endpoint will be analyzed for exploratory purpose only.
 
Safety analysis:
 
Safety analysis will be descriptive, based on the safety population. Safety analysis will focus on the Treatment Emergent Adverse Events (TEAE) period defined as the time from the day of randomization to the last administration + 21 days (3 weeks), or end of study, whichever comes first.
 
The treatment arm allocation for as-treated analysis will be defined as follows:
 
• Alirocumab arm if proportion of IMP injection is $\geq 50\%$.• SoC arm if proportion of IMP injection is $< 50\%$. 
where proportion of IMP injection (%) is defined as:
 $100 \times (\text{Number of IMP injection}) / [(\text{Date of end of treatment} - \text{Date of randomization}) / 14 + 1]$
DURATION OF STUDY PERIOD (per patient)	9 months

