9.2 SAFETY ENDPOINTS

Safety endpoints are as follows:

- Safety parameters (adverse events including CV events, laboratory data, and vital signs) will be assessed throughout the study.

Note: CV events include CHD death, non-fatal MI, fatal and non-fatal ischemic/hemorrhagic stroke, congestive heart failure requiring hospitalization, ischemia-driven coronary revascularization procedure.

The observation period of safety data is defined in [Section 11.4.3](#).

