9.2.1 Adverse events

All AEs diagnosed by the Investigator/sub-Investigator, irrespective of the result of the adjudication for CV events, will be reported and described.

- All AEs will be coded to “Lowest Level Term (LLT)”, “Preferred Term (PT)”, “High Level Term (HLT)”, “High Level Group Term (HLGT)”, and associated primary “System Organ Class (SOC)” using the version of Medical Dictionary for Regulatory Activities (MedDRA) currently in effect at Sponsor or delegate at the time of the considered database lock.
- AESIs include events as the following:
 - General allergic events (refer to [Section 10.6.2](#))
 - Local injection site reactions (using specific e-CRF pages, refer to [Section 10.6.1](#) and [Section 17](#), Appendix I)
 - Hemolytic anemia (using specific e-CRF pages, refer to [Section 10.4.4.1](#) and [Section 17](#), Appendix H)
 - Neurologic and Neurocognitive adverse events (refer to [Section 10.4.4.1](#) and [Section 17](#), Appendix F)
 - Ophthalmologic adverse events (using specific e-CRF pages, refer to [Section 10.4.4.1](#) and [Section 17](#), Appendix F)
 - Skeletal muscle-related adverse event (using specific e-CRF pages, refer to [Section 17](#), Appendix F)
 - Symptomatic overdose with IMP (refer to [Section 10.4.4.1](#) and [Section 17](#), Appendix F and G)

- Pregnancy (including male patient's partner) (refer to [Section 10.4.4.1](#) and [Section 17](#), Appendices A and F)
- Elevation of ALT (refer to [Section 10.4.5](#) and [Section 17](#), Appendices F and G)

Adverse event observation period is as per observation period of safety data defined in [Section 11.4.3](#).

Adjudicated CV events include all CV AEs and coronary revascularization positively adjudicated (refer to [Section 10.6.3](#)) occurring after obtaining the informed consent for study participation until the end of study. The adjudication classifications are the following:

- CHD death
- Non-fatal MI
- Fatal and non-fatal ischemic and/or hemorrhagic stroke
- Unstable angina requiring hospitalization
- Ischemia-driven coronary revascularization procedure

In addition, all deaths will be classified.

Note: Observation period for death are as per the adverse event observation period. In addition, “post-study” death includes all deaths reported after the end of the study (refer to definition of end of study per patient in [Section 6.2.2](#)).

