10.6.3 Cardiovascular events and all deaths

The following suspected or confirmed CV events that occur from randomization until end of the study visit should be reported in a corresponding specific e-CRF. The Investigator will submit the adjudication materials to the CEC through the Sponsor as needed:

- MI.
- Congestive heart failure requiring hospitalization.
- Cerebrovascular events (e.g., stroke, transient ischemic attack, intracranial hemorrhage, ischemia or bleeding of spine or retina).
- Unstable angina requiring an emergency room visit or requiring / prolonging hospitalization.
- All coronary revascularization procedures (e.g., PCI, coronary artery bypass graft).
- All death (including CHD death).

All suspected or confirmed CV events should be reported as SAEs. For coronary revascularization procedures, medical or surgical procedure should not be reported as an adverse event, but rather, the reason for the procedure should be reported as the adverse event (e.g., unstable angina leading to PCI should be reported as “unstable angina” instead of “PCI”).

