11.4.3.1 Adverse events

The adverse events are defined as follows:

- Pre-treatment AEs are AEs that develop, worsen, or become serious during the pre-treatment period
- TEAEs are AEs that develop, worsen, or become serious during the TEAE period
- Post-treatment AEs are AEs that develop, worsen, or become serious during the post-treatment period

AE incidence tables will be presented by SOC (sorted by internationally agreed order), HLT, HLT, and PT sorted in alphabetical order for each treatment arm, and the number (n) and percentage (%) of patients experiencing an AE. Multiple occurrences of the same event in the same patient will be counted only once in the tables within a treatment phase. The denominator for computation of percentages is the safety population within each treatment group.

AE incidence table will be provided by treatment arm for all types of TEAEs: all TEAEs, all treatment emergent AESI (defined with a PT or a prespecified grouping), all treatment emerged SAEs, and all TEAEs leading to permanent treatment discontinuation.

Deaths

The following deaths summaries will be generated:

- Number (%) of patients who die during study period (TEAE, on-study, post-study) summarized on the safety population by treatment received

- Death in non-randomized patients or randomized and not treated patients
- TEAE leading to death (death as an outcome on the AE CRF page as reported by the Investigator/sub-Investigator) by primary SOC, HLGT, HLT, and PT showing number (%) of patients sorted by internationally agreed order of SOC and alphabetic order of HLGT, HLT, and PT.

Adjudicated CV events

The number and percentage of patients experiencing a positively adjudicated CV event will be presented by treatment arm overall and by category of adjudication.

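### The SAP limits adjudicated cardiovascular events to the treatment-emergent window and lists ischemic stroke only, whereas the protocol counts them to end of study and includes hemorrhagic stroke

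*SAP*

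**What the plan says.** **Protocol, period.** Section 9.2.1 defines adjudicated CV events as those positively adjudicated and "occurring after obtaining the informed consent for study participation until the end of study". Section 11.4.3.1 plans the number and percentage of "patients experiencing a positively adjudicated CV event will be presented by treatment arm overall and by category of adjudication", and sets no treatment-emergent limit. The safety objective (Protocol 5.2, repeated in SAP 1.2.2) covers CV events over the whole study.

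**Protocol, stroke.** The adjudication classes in 9.2.1 include "Fatal and non-fatal ischemic and/or hemorrhagic stroke". The CV event definition in the synopsis has "fatal and non-fatal ischemic and/or haemorrhagic stroke", and section 9.2 has "fatal and non-fatal ischemic/hemorrhagic stroke".

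**SAP.** Section 2.1.4.1 sends suspected events to the Clinical Event Committee (CEC) from randomization until the follow-up visit. It then names six categories to be described: CV death, myocardial infarction, ischemic stroke, unstable angina, heart failure and ischemia-driven revascularization. The only analysis statement, in 2.4.5.1, is "Adjudication results of treatment-emergent CV events will be summarized". SAP 2.1.4 ends the treatment-emergent period 21 days after the last study treatment or at end of study, whichever is earlier. The same section also defines an on-study period from randomization to end of study.

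**The concern.** The SAP collects and adjudicates events over a wider period than it analyses, and over a narrower set of stroke types than the protocol's endpoint definition. SAP 1.6 and Table 1 in SAP 1.7 describe changes and adaptations, and Table 1 records that heart failure was added to adjudication. Neither mentions a shorter window or a dropped stroke type.

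What is at stake is the adjudicated count by category that Protocol 11.4.3.1 promises. A programmer who follows the SAP would leave a late non-fatal event out of the adjudicated table and would have no listed row for a non-fatal hemorrhagic stroke. A reader of the report could take that table to cover the whole study.

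**Working it through.** The plan states no figure on this point, so the check compares the texts and then sizes the gap.

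**Texts side by side**

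| Item | Protocol | SAP |
|---|---|---|
| Period | 9.2.1: consent to end of study. 10.6.3: reporting from randomization to the end-of-study visit | 2.1.4.1: submission from randomization to the follow-up visit. 2.4.5.1: summary of treatment-emergent events only |
| Summary | 11.4.3.1: number and % by arm, overall and by category | 2.4.5.1: adjudication results, layout not stated |
| Stroke | Synopsis endpoint, 9.2 and 9.2.1: ischemic and hemorrhagic. 5.2 and 6.4: ischemic only | 1.2.2 and 2.1.4.1: ischemic only |

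**Days outside the window.** Inputs are the nominal days in the flow chart (Week 34 = Day 239, Week 36 = Day 253, so Week 38 = Day 267) and the 21 days in SAP 2.1.4. Suppose that study treatment means the injections. A last injection at Week k falls on Day 7k + 1, and the window ends on Day 7k + 22. Days lost up to Day 253 are 253 − (7k + 22) = 231 − 7k, or zero if that is negative.

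- k = 0: 231 days
- k = 10: 231 − 70 = 161 days
- k = 22: 231 − 154 = 77 days
- k = 34: the window ends on Day 260, so 0 days are lost to Day 253 and 7 to Day 267
- k = 36 (extra dose): the window ends on Day 274, so none are lost

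**Events lost among 100 alirocumab patients.** Events = 100 × p × r × d / 365.25, where p is the share stopping early, r the yearly event rate and d the days lost. Protocol 4 gives r = 0.10 for CV death, myocardial infarction or stroke within a year of an acute coronary syndrome. It also gives 4.9% stopping for an adverse event over 52 weeks in the Japanese phase 3 study. Scaled to 36 weeks that is 4.9% × 36/52 = 3.4%. The stop weeks, the 10% upper value for p, a constant rate and full follow-up after stopping are assumptions.

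- p = 3.4%, d = 77: 100 × 0.034 × 0.10 × 77/365.25 = 0.07
- p = 4.9% (unscaled), d = 161: 100 × 0.049 × 0.10 × 161/365.25 = 0.22
- p = 10%, d = 231: 100 × 0.10 × 0.10 × 231/365.25 = 0.63

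At the same rate, about 100 × 0.10 × 252/365.25 = 6.9 events would be expected in the arm over 252 days. The third case is extreme, since every stopper leaves after one injection. Even there, losing one event needs a yearly rate of 0.10/0.63 = 16%.

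The rate could be too high: it includes deaths, which are reported elsewhere, and Protocol 4 notes lower CV event rates in Japan. It could be too low: it omits unstable angina, heart failure and revascularization.

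If study treatment includes a statin that continues, the window stays open and the loss is near zero. The missing stroke category does not depend on any of this arithmetic, and the documents give no rate for hemorrhagic stroke.

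**The case against.** **The protocol itself looks to the treatment-emergent period.** The synopsis says "Safety analysis will focus on the Treatment Emergent Adverse Events (TEAE) period". That is a general focus. Sections 9.2.1 and 11.4.3.1 deal specifically with adjudicated CV events and carry no such limit, so the mismatch remains.

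**The charter governs.** Protocol 6.4 leaves the events for adjudication to the CEC charter, and SAP 2.1.4.1 defines positive adjudication by that charter. The six SAP categories match the stroke wording of the safety objective. This stands in part. A reader might infer that hemorrhagic strokes will never be adjudicated or shown. The documents do not support that, because the charter may provide for them and the sentence in 2.4.5.1 is not confined to the six categories.

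**The events appear elsewhere.** A reader might infer that late events vanish from the report. They do not. Protocol 10.6.3 makes CV events reportable as serious adverse events, and SAP 2.4.5.1 tabulates treatment-emergent and post-treatment serious events by preferred term. SAP 2.4.5.2 gives CEC-adjudicated reasons for death, on-study deaths included. Only the adjudicated count of non-fatal events by category is lost.

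**Follow-up may close early.** Protocol 10.4.2 continues observation after treatment stops, and 10.3.4 asks patients who stop treatment to keep the visit schedule to Week 36. But 10.3.4 also brings end-of-treatment assessments forward for those who discontinue the study. If that ends follow-up, the 21-day window loses nothing for them. This stands and lowers the estimate.

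**The nominal days are not strict bounds.** Injections have a ±7-day window, so the 0 to 7 days could be exceeded. The Week 36 dose for late imaging works the other way. Follow-up extended for an ongoing serious event (Protocol 6.2.1) would add days.

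**Silence in the change sections proves little alone.** SAP 1.5 records changes to the protocol's own statistical section, so nothing follows from it. SAP 1.7 covers major adaptations only.

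**Conclusion.** The discrepancy is real on the text, and its effect is small. The SAP would tabulate adjudicated CV events over a shorter period than Protocol 9.2.1 and 11.4.3.1 set out, and its category list omits a stroke type named in three places in the protocol.

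Patients injected to Week 34 lose about 0 to 7 days at nominal visit days. Early stoppers who remain in follow-up can lose much more, but this probably amounts to fewer than one event in the trial. That estimate rests on the injection reading of study treatment and on the assumed stopping pattern, event rate and follow-up.

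Two stronger conclusions are not supported:

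- **A biased safety comparison.** The arms could be counted over unequal periods only if study treatment means the injections. The expected difference is slight, and Protocol 11.4.3 plans no safety testing.
- **A known excess of hemorrhagic stroke.** Protocol 4 speaks of higher cerebrovascular event rates in Japan, not of hemorrhagic stroke, and exclusion E 03 removes patients with a known history of it.

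Severity is minor: the two documents should be reconciled.

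**What to change.** 1. **SAP 2.4.5.1.** Tabulate the number and percentage of patients with a positively adjudicated CV event by arm, overall and by category, over the on-study period already defined in SAP 2.1.4. Keep the treatment-emergent table as supplementary.
2. **SAP 2.1.4.1.** Add a hemorrhagic stroke category to match the protocol synopsis endpoint, 9.2 and 9.2.1. Reconcile it with the CEC charter and with Protocol 5.2 and 6.4, which name ischemic stroke only.
3. **SAP change section.** Record both edits.

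A listing of events between consent and randomization is not needed. Protocol 9.2.1 starts counting at consent, but site reporting (Protocol 10.6.3) and submission to the CEC (SAP 2.1.4.1) start at randomization.

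The cost is one table and one row. The on-study table needs no new collection, because Protocol 10.6.3 already requires reporting to the end-of-study visit. If the charter does not cover hemorrhagic stroke, the new row would also need a charter change and adjudication of any such events.

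Which drug's date counts as the last study treatment affects every treatment-emergent table and should be handled as a separate point.
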